Other researchers explored the use of Campath® as an immunosuppressive agent for renal transplantation. The first was Stuart Knechtle at the University of Wisconsin who combined Campath® with monotherapy Rapamune® instead of cyclosporine as was done in Cambridge. Stuart Knechtle reasoned that Rapamune® rather than a calcineurin inhibitor such as cyclosporine might allow for tolerance mechanisms leading to graft acceptance following lymphocyte depletion (in fact, this work was funded by the Immune Tolerance Network). This idea was based on work in mice that supported this concept.⁷ Therefore, rather than using half-dose cyclosporine monotherapy as had been successfully done in the Cambridge trial, Knechtle tried using Rapamune® monotherapy post-operatively. Campath® induction with 40 mg total dose was used in 29 primary human renal transplants and the patients were maintained on Rapamune® monotherapy (levels 8-15 ng/mL) post-transplantation. They found that Campath® profoundly depleted T- lymphocytes long-term and more transiently depleted B cells and monocytes. Unfortunately, there was a high rejection rate (8 of 29, 28%) with this combination with many of the rejections being a humoral rejection (5 of 8, 63 %) and one of these resulting in a graft loss.⁸ All patients were alive and well after 3-29 months of follow up. One graft was lost because of rejection and seven of the 29 patients were converted to standard triple therapy on account of rejection. There were no systemic infections and no malignancies.

Allan Kirk at the NIH used Campath-1H alone without any subsequent immunosuppression in an attempt to induce tolerance. He did not see rejection for the first several weeks but then by the end of the first month or second month all the patients had rejections that were responsive to steroids and the initiation of Rapamune®. Interestingly, all of the rejections showed no evidence of lymphocytic infiltration on biopsy. Instead, macrophages appeared to be responsible for the rejection.⁹ For this reason, Allan Kirk performed a follow-up study where he used deoxyspergualin as an anti-macrophage immunosuppressant post transplantation with Campath-1H induction. Unfortunately, this set of patients fared no better than the initial seven patients he had treated with Campath-1H alone.¹⁰

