Peter Friend added another study to the Campath® story with a multi-center trial carried out in collaboration with Stuart Flechner at the Cleveland Clinic.¹⁵ They performed a pilot study in which 22 kidney recipients (14 LD: 8 DCD) were given Campath® induction (30 mg day 0 and 1), steroids (500 mg mp day 0 and 1, none thereafter), Cellcept® (MMF) maintenance (500 mg b.i.d) and sirolimus (concentration controlled 8-12 ng/mL). With a mean follow-up of 15.9 months, patient survival was (21/22) 96% and graft survival (19/22) 87%. Acute rejections occurred in (8) 36.3% (two humoral). Of 19 surviving grafts, 18 (95%) remained steroid and 15 (79%) CNI-free. At 1 year, mean creatinine was 1.43 mg/dL. Overall infection rates were low, but 2 patients

developed severe acute respiratory distress syndrome (ARDS) at month 3 and 7, respectively, resulting in mortality in one and a graft loss in the other. No cancer or PTLD was observed. Leukopenia was common and MMF dose was reduced or eliminated in 6/22 (27%) patients. The reported higher than expected rate of acute rejection, leukopenia and possible pulmonary toxicity suggested excessive morbidity and the authors suggested that modifications such as an initial period of CNJ use should be considered.

Another group to make an important contribution to the Campath® literature has been led by Ron Shapiro at the University of Pittsburgh and their protocol is explored in further detail as it served as the model for the initial use of Campath® at the University of Toledo (except of spaced weaning of Prograf®). Pittsburgh used Campath-1H as induction as only one dose on day zero. The dose was 0.5 mg/kg for patients up to the weight of 60 kg. Any patient whose weight is ≥ 60 kg is given a total dose of 30 mg Campath-1H intravenously. Recipients were pre-medicated with Tylenol® 650 mg PO, Benadryl® 25 mg IV, Pepcid® 20 mg IV and Methylprednisolone 1 gram IV. A second dose of Methylprednisolone was given just before the arterial clamps were removed. No further steroids were administered. The patients were given monotherapy Prograf® post-operatively aiming to keep the level at about 10 ng/ml for the first 4 months and then patients were slowly weaned to lower Prograf® doses with 62% of the patients being successfully weaned to every other day Prograf® dosing.

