After publication of the study by Hanaway et al. in NEJM in late 2011, we decided that our 15-20% rejection rate with Prograf® and myfortic® with no steroid taper was unacceptable.¹⁸ Therefore, we modified our protocol to eliminate the second dose of 500 mg methylprednisolone intraoperatively and instead have spread this out by adding a steroid taper for the first five days post-operatively as was done in the Hanaway study. Since adopting this policy, we have seen a significant reduction in our rejection rate.

Everolimus (Zortress®) inhibits the proliferation (growth or production) of T and B cells. It is an inhibitor of intracellular signal transduction (the relaying of signals inside a cell that communicates to the cell that it should activate or change) that targets the

mammalian target of rapamycin (mTOR). The mechanism of action of everolimus appears to be distinct from those of calcineurin inhibitors. It forms a complex with the cytoplasmic protein FKBP-12 (intracellular tacrolimus-binding protein) and binds to and interferes with the function of FRAP. FRAP is a key regulatory protein which governs cell metabolism, growth and proliferation. The blockage of this signal leads to inhibition of cell cycle progression from G1 to the S phase (cell cycle growth phases); thus not allowing cells to develop and multiply. Combining everolimus and a calcineurin inhibitor gives rise to synergistic immunosuppressive properties.

Tacrolimus (Prograf® or Hecoria®) inhibits T-lymphocyte activation, although the exact mechanism of action is not known. Experimental evidence suggests that tacrolimus binds to an intracellular protein, FKBP-12. A complex of tacrolimus-FKBP-12, calcium, calmodulin, and calcineurin is then formed and the phosphatase activity (enzyme that frees or removes phosphate from a chemical reaction) of calcineurin is inhibited. This effect may prevent the dephosphorylation (removal of a phosphate group) and translocation (chromosome rearrangement) of nuclear factor of activated T-cells (NF-AT), a nuclear component thought to initiate gene transcription for the formation of lymphokines (substances released by activated T-cells such as interleukin-2 or gamma interferon). The net result is the inhibition of T-lymphocyte activation (i.e., immunosuppression).

Study Purpose and Rationale

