 - Adequate barrier methods of contraception include: diaphragm, condom (by the partner), intrauterine device (copper or hormonal), sponge or spermicide. Hormonal contraceptives include any marketed contraceptive agent that includes an estrogen and/or a progestational agent. Acceptable contraception methods will be discussed with all women of child-bearing potential.

- Reliable contraception should be maintained throughout the study and for 8 weeks after study drug discontinuation. For women who become pregnant while using Myfortic® or within 8 weeks of discontinuing therapy, we will report the pregnancy to the Mycophenolate Pregnancy Reference Registry ([name]) and will strongly encourage the patient to enroll in the pregnancy registry.
- Women are considered post-menopausal and not of child bearing potential if they have had 12 months of natural (spontaneous) amenorrhea with an appropriate clinical profile (e.g. age appropriate, history of vasomotor symptoms) or six months of spontaneous amenorrhea with serum FSH levels > 40 mIU/mL and estradiol < 20 pg/mL] or have had surgical bilateral oophorectomy (with or without hysterectomy) at least six weeks ago. In the case of oophorectomy alone, only when the reproductive status of the woman has been confirmed by follow up hormone level assessment is she considered not of child bearing potential.

Study Duration:

We plan to enroll 11 patients per year. Given this assumption, the enrollment will take five years. Adding two years of follow-up care, we will be able to complete the study in 7 years.

Study Design:

1. Single center pilot study utilizing historical control
2. A single treatment arm
3. Eleven patients per year
4. Five years to enroll 55 patients.
5. Enroll all patients who meet the inclusion criteria at 2 months and up to 6 months (± 10 days) post kidney transplantation and are willing to consent for this trial.
6. Patients would have study visits, serum creatinine measurements and other clinically relevant parameters measured monthly until 6 months, then q3 months until 2 years post-transplantation.
7. Graft survival would be measured by the absence of the need for dialysis.
8. It would not be mandatory, but a renal biopsy would be recommended at 2 years to look for underlying early signs of calcineurin toxicity/chronic allograft nephropathy.

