12. If delayed graft function is suspected, tacrolimus may be held for the first few days until the creatinine level begins to fall spontaneously.
13. Target tacrolimus levels for the first 2 months post-operatively will be 10-12 ng/ml with a target level goal of 10 ng/ml. After three months, the standard of care approach calls for the tacrolimus target level to be reduced to 8-10 ng/ml (with a target level of 8 ng/ml) until the end of the first year. After the first year, patients without evidence of rejection would have their tacrolimus dose reduced to achieve a trough level of 6-8 ng/ml (with a target level of 6 ng/ml). This approach was used for patients in the historical control arm.
14. No patients are to be treated for rejection without first obtaining a renal biopsy to confirm a cellular or humoral rejection.
15. Cellular rejections scored as Banff 1 will be treated with three, daily pulses of 250-500 mg methylprednisolone on three consecutive days and by confirming a therapeutic level of tacrolimus. Cellular rejections scored as Banff 2 or for those rejections that are not responsive to steroids alone, Thymoglobulin® will be used for a 10-14 day course. Depending on the level of rejection,

- ongoing steroid therapy can be administered after agreement by the treating physicians. Generally, hospitalization is required for at least the first few days of the treatment of rejection using Thymoglobulin®. During the first dose of Thymoglobulin®, blood pressure and vital signs will be monitored every 15 minutes for the first hour, then every 30 minutes for the next two hours, then every one hour for the next 3 hours and then per routine protocol if stable.
16. Humoral rejections will be treated with IVIG 100 mg/kg followed by a one volume exchange plasmapheresis on an every other day basis until the creatinine begins to fall or a decision is made to hold off on further treatment. In extreme cases, re-dosing Campath® can be considered or use of the anti-B cell agent, Rituximab (anti-CD20) can be used. These decisions will be made after consultation between the transplant surgeon and attending nephrologists.
 17. The intention-to-treat concept will be applied to patients who experience biopsy-proven rejection to avoid missing outcomes. For patients in the study, low-dose myfortic® may be added back to the patient's immunosuppression regimen. Short-term treatment with oral corticosteroids may be required, but long-term steroid use will be avoided.

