This will be a small, pilot study to test whether conversion to everolimus (Zortress®), allowing the reduction of calcineurin inhibitors, will reduce nephrotoxicity (measured by increased creatinine clearance) and lengthen overall graft survival (measured by 2-3 year graft survival). As it is not a large study (55 patients, 11 patients per year), it is not powered to achieve statistical significance. The statistical significance will also be impaired by the use of a historical control group. However, the data generated will be published irrespective of the results, thus making the data available for meta-analysis.

This trial is designed as a parallel-group study. Analysis of data for this design is simple and interpretation of the result is straightforward. Given the limited number of

patients in the trial it may not be meaningful to apply analysis of (co)variance for the statistical evaluation of a continuous variables such as creatinine clearance, but we will attempt to use this method with the guidance of our statistician, [name].^{19,20} Likewise, the limited number of patients in the trial may prevent meaningful analysis of time-to-event variables such as graft survival. Nonetheless, we will work with [name] to use methods appropriate for survival analysis including the Kaplan-Meier method and Cox's proportional hazards regression to see if meaningful differences exist between our study groups and our historical control.^{21,22} If warranted, for safety analyses the AEs and SAEs could be summarized by treatment group but no statistical tests performed due to the population size as a pilot study. In addition, the PI and Co-PI will meet with other members of the clinical transplant team to review the results of this study on a quarterly basis to ensure that no significant adverse events warrant the discontinuation of the trial. Given the small number of patients in the trial, we will analyze the data after we have enrolled 10 patients. If the study immunosuppression regimen has a > 40% Banff 2a rejection rate or greater than 20% patient death rate, then that arm will be prematurely terminated. Serious adverse events will also be analyzed and may serve as grounds for study discontinuation.

Everolimus IIRP Pilot Study Evaluation and Visit Schedule

Treatment Period															
			Months												
	Screening (Visit 1)	Baseline (Visit 2)	1 (3)	2 (4)	3 (5)	4 (6)	5 (7)	6 (8)	9 (9)	12 (10)	15 (11)	18 (12)	21 (13)	24 (14)	

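### The only numeric rejection limit (at least 5 of 10 with Banff 2a) is unlikely to act at rejection rates the protocol calls unacceptable or high; a lower running pause rule would be a cheap, modest addition

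*Combined protocol and SAP*

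**What the plan says.** The Statistical Section states: "we will analyze the data after we have enrolled 10 patients". The rejection condition is "If the study immunosuppression regimen has a > 40% Banff 2a rejection rate"; a parallel condition is a death rate above 20%. Either one ends the arm. The section gives no minimum follow-up for the 10 patients, no chance of crossing, and no lower level at which conversion would pause. It does provide for quarterly review by the clinical team and allows serious adverse events to be grounds for stopping.

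Study Duration gives the accrual rate: "We plan to enroll 11 patients per year".

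Background and Preliminary Data shows what the protocol regards as too much rejection. On the centre's own earlier regimen: "we decided that our 15-20% rejection rate with Prograf® and myfortic® with no steroid taper was unacceptable". It calls 8 of 29 a high rate in a Campath and sirolimus monotherapy series. It reports 8 of 22 in a Campath, sirolimus and mycophenolate pilot, with the comment: "The reported higher than expected rate of acute rejection, leukopenia and possible pulmonary toxicity suggested excessive morbidity". All of these count rejection of any grade.

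The detailed management protocol uses Banff grades for cellular rejection (item 15: "Cellular rejections scored as Banff 2 or for those rejections that are not responsive to steroids alone" leads to Thymoglobulin). It deals with humoral rejection in a separate item (16).

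**The concern.** The study withdraws myfortic and lowers the tacrolimus target to 3-5 ng/ml in patients without maintenance steroids. Rejection is therefore the foreseeable harm, and treated biopsy-proven rejection is part of a co-primary endpoint. The one rejection number fixed in advance is high, is restricted to a severe grade, and is tied to a date when most of the 10 patients have been followed for less than six months.

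If rejection after conversion ran at rates the protocol calls unacceptable or high, this limit would usually stay silent. Whether to keep converting patients, up to 55, would then rest on discretionary review, with no count that obliges anyone to pause and record a decision.

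**Working it through.** The plan gives no operating characteristic for the limit, so there is no stated figure to reproduce.

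**Limit as a count.** 0.40 × 10 = 4, and 4 of 10 is exactly 40%, which is not above it. Crossing needs 5 of 10.

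**Rates used.** All come from Background and Preliminary Data.
- 15.6%: the centre's one-year rate on tacrolimus and myfortic (19.8% at two years).
- 20%: the top of the range called unacceptable. It is close to the two-year figure, so using it as a 12-month risk is an assumption.
- 8/29 = 27.6%: follow-up of 3-29 months.
- 8/22 = 36.4%: mean follow-up of 15.9 months.

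All run from transplantation, whereas study patients must be rejection-free at entry. Treating any of them as a 12-month post-conversion risk is an assumption.

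**Existing limit, complete follow-up.** P(X ≥ 5) = Σ C(10,k) p^k (1−p)^(10−k) for k = 5 to 10. At p = 0.20: 0.0264 + 0.0055 + 0.0008 + 0.0001 = 0.0328. Counting every rejection as Banff 2a makes this an upper bound.

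**Existing limit at the tenth enrolment.** With even accrual of 11 per year, patient i has (10 − i) × 12/11 months of follow-up: 9.8 months for the first, none for the tenth, mean 4.9. With constant hazard h = −ln(1−p)/12, each patient's risk is 1 − exp(−h × months). The count is then a sum of unequal Bernoulli variables. At p = 0.20 the expected number of events is only 0.86.

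| True 12-month rate | 5 of 10, complete follow-up | 5 of 10, day of tenth enrolment |
|---|---|---|
| 15.6% | 1.2% | 0.02% |
| 20% | 3.3% | 0.05% |
| 8/29 | 11.2% | 0.3% |
| 8/22 | 27.9% | 1.0% |

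Constant hazard may flatter the last column. One Campath series in the Background had 2% rejection by 6 months, 9% by 12 and 19.5% by 24.

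**If humoral rejections do not count.** Five of 8 rejections were humoral in the 29-patient series and 2 of 8 in the 22-patient pilot. That leaves 3/29 and 6/22, for which P(X ≥ 5) with complete follow-up is 0.2% and 11%.

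**A pause at 3 of 10, any type or grade, within 12 months of conversion.** P(X ≥ 3) = 1 − P(0) − P(1) − P(2). At p = 0.20: 1 − 0.1074 − 0.2684 − 0.3020 = 0.322. If p is a 24-month risk, the 12-month risk is 1 − √(1−p): 0.106, 0.149 and 0.202 for the last three rows.

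| Rate p | p as 12-month risk, full follow-up | p as 24-month risk, full follow-up | p as 12-month risk, day of tenth enrolment |
|---|---|---|---|
| 5% | 1% | – | – |
| 10% | 7% | – | – |
| 15% | 18% | – | – |
| 15.6% | 20% | – | – |
| 20% | 32% | 8% | 4% |
| 8/29 | 55% | 18% | 10% |
| 8/22 | 77% | 33% | 21% |

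The last column shows why the rule must be a running count rather than a single look. In 400,000 simulated trials under the 12-month reading, the median number enrolled when it fires is 13, 12 and 11 at the last three rates, and never more than 20 of 55. The latest possible trigger is at 9 × 12/11 + 12 = 21.8 months.

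**The case against.** The strongest reply is that a termination limit on a severe cellular grade need not sit below any-grade rates, and that monitoring does not depend on it. Banff 2 or steroid-resistant rejection is treated with Thymoglobulin, generally in hospital. Hospitalization is a seriousness criterion, and SAEs go to the sponsor within 24 hours. Events possibly related to the regimen reach the IRB within 7 days, and the IRB can end approval. The team meets quarterly, and myfortic may be restored after a rejection. All of this stands. A reader might infer that the limit is a mistake or that rejection is unmonitored; the documents support neither. What remains is that none of these routes names a rejection level.

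The benchmarks are also imperfect. The two sirolimus series began without a calcineurin inhibitor, and the excess-morbidity remark about the 22-patient pilot was a joint judgement on rejection, leukopenia and possible lung toxicity. These rates show what the protocol regards as high; they do not forecast this regimen.

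Two further inferences go too far. The limit is not rarely met at every rate: at 8/22 with complete follow-up it is met more than a quarter of the time. Nor does the text say that humoral rejection is excluded, that Banff 2a means only that grade, or that the limit lapses after the tenth enrolment. Those are open readings.

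Finally, the pause rule is weak at the locally relevant rates: it misses about two-thirds of cases at 20%, and 92% if that is a 24-month risk. That is correct and limits the claim.

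**Conclusion.** The point holds as an optional improvement, not as an error. The limit is unlikely to act at 15.6%, 20% or 8/29 (1.2%, 3% and 11% as upper bounds). It acts about one time in four at 8/22 (28%), and about 1% of the time or less at any of these rates on the day the tenth patient enrols. The complete-follow-up figures rest on independent patients and on counting every rejection as Banff 2a. The early figures also assume even accrual and constant hazard. The 20%, 28% and 36% rates are assumptions, because their sources run from transplantation over other follow-up periods.

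A pause at 3 of 10 raises the chance of a forced decision to 20% at 15.6%, 32% at 20%, 55% at 8/29 and 77% at 8/22. It is much lower if the last three are 24-month risks (8%, 18% and 33%). The gain is modest and covers only the first 10 patients.

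**What to change.** Keep both termination limits in the Statistical Section and add: *Counted continuously from conversion, if 3 or more of the first 10 converted patients have treated biopsy-proven rejection of any type or grade within 12 months of conversion, no further patient is converted until the review group has met and recorded a decision to continue, modify or stop.*

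Beside it, print the chance of a pause with full follow-up at assumed 12-month post-conversion risks: 1% at 5%, 7% at 10%, 18% at 15%, 20% at 15.6%, 32% at 20%, 55% at 28% and 77% at 36%. Add that the last three become 8%, 18% and 33% if those rates are 24-month risks, and that the 20%, 28% and 36% rates are themselves assumptions.

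The cost is one sentence and a short table. No new data are needed: biopsy already precedes rejection treatment (management protocol, item 14), and the visit schedule has a rejection record at every visit. A needless pause occurs about 1% of the time at a true rate of 5% (the 12-month Campath rate in the randomized trial cited in the Background) and 7% at 10%. Pauses at 15-18% should not be called needless, since the protocol calls 15-20% unacceptable. If the group waits for its next quarterly meeting, the delay is about 3 enrolments at most (11/4 = 2.75). Later patients stay under the existing quarterly, SAE and IRB review.
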